5.3.1.3 Clinical safety studies

In 1999, a phase I study was conducted to evaluate the safety of three DFBA formulations, at 0.002%, 0.01% and 0.05% in 18 healthy subjects. The intervention consisted of a single drop of the product under investigation in one eye, and in the contralateral one drop of the vehicle. Evaluation of the ocular surface and an electroretinogram were performed 24 hours after instillation. The tolerability and symptomatology was evaluated through questioning by means of a questionnaire. Adverse events (AEs) reported were mild and not necessarily related to instillation. [44]

In another phase I study, two concentrations of DFBA, 0.01% and 0.05%, were evaluated in 12 subjects. The intervention consisted in the application of two drops of the investigational drug four times a day for 7 days, in one eye, and in the contralateral vehicle. The results of this study showed that either of the two formulations was well tolerated and had little systemic effects. EAs were mild, PIO increased three times, but none of them exceeded normal limits. [44]

At Sophia Laboratories, a phase I study was conducted comparing the PRO145 emulsion against Durezol® and placebo, with an application of 1 drop qid for 10 days, continuing with a bid drop for 5 days, in both eyes. We included 27 healthy subjects, randomly divided into 3 groups corresponding to the 3 interventions. Symptoms and clinical signs, including PIO, were evaluated. In addition, laboratory tests, QS, BH and liver enzymes were performed. No statistically significant differences were found between groups. No increase in PIO was reported in any of the subjects. It was concluded that the safety profile of PRO-145 in equal circumstances is similar to that of Durezol®. [45]

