5.4 Justification

Control and prevent inflammation is one of the main concerns of the ophthalmologist surgeon to achieve optimal results after surgery.

Steroids are the drugs of first choice for the control of inflammation due to its broad anti-inflammatory activity and its safety profile.

PRO-145 is a formulation of 0.05% DFBA in ophthalmic emulsion, developed by Sophia Laboratories, S.A. of C.V. which has demonstrated an acceptable safety profile in preclinical and clinical phase I studies, as well as a bioavailability in animal models similar to that reported for Durezol®. With this background, a phase III clinical study is required to verify the efficacy profile of PRO-145.

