5.5.4 Hypothesis

H0: The use of the ophthalmic emulsion PRO-145 is not effective when decreasing the inflammatory response evaluated by means of cellularity in the anterior chamber, after phacoemulsification.

Ha: The use of the ophthalmic emulsion PRO-145 is effective in decreasing the inflammatory response evaluated by means of cellularity in the anterior chamber, after phacoemulsification.

5.6 Design and plan of the study.

Phase III clinical trial, parallel, controlled, randomized, double blind. Participants will be postsurgical phacoemulsification patients, who will be randomly assigned to 2 intervention groups with steroidal anti-inflammatory drugs. One group will receive the PRO-145 test formulation and the other group will be exposed to prednisolone acetate 1%.

[figure not shown]

Figure 2. Study design.

5.6.1 Discussion of the study design.

In clinical research it is common to propose trials with the objective of evaluating the efficacy of a product under investigation against a reference medicine or active control, in order to compare the new product under investigation from a clinical or statistical point of view to a drug commercially available

The clinical trial is the ideal model to evaluate the effectiveness of two interventions, it allows obtaining the highest quality evidence among different types of research. The characteristics of randomization and double blind, allow to avoid biases (selection, evaluation, etc.) that can not be avoided with other models. Being controlled and parallel groups allows distinguishing the effects of interventions in isolation.

The proposed clinical trial aims to evaluate the efficacy, safety and tolerability profile of a formulation of DFBA 0.05% and compare it against the safety, tolerability and efficacy profile of commercially available steroid administration, and widely used for its efficacy profile and known security.

6. Material and methods. Participants, interventions and variables.

6.1 Study Center.

The present study will be performed in ophthalmology offices duly equipped and registered for their proper functioning. According to the needs of the sponsor, these may be private or public, be attached to a hospital or clinic or be independent.

This is a multicentre study that is intended to be carried out in Guadalajara, Mexico City and Monterrey.

6.1.1 Organization of the center.

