6.5.3 Diagram of the study

[figure not shown]

Figure 4. Diagram of the study

6.6 Sample size.

The sample size calculated for the present study is 178 subjects.

Divided into two intervention groups, each group will be comprised of 89 subjects. Each subject will provide an eye for efficacy analysis.

6.6.1 Calculation of the sample size.

The sample size was calculated using the formula for two proportions variables as well as the data was entered into the online calculator, software developed in: www.powerandsamplesize.com based on Chow S et al. [72]

With a statistical confidence of 95% corresponding to the type I error, equal to 1.96, with a power of 80%, corresponding to the type II error, equal to 0.84. A 78.9% efficiency ratio was considered in the reduction of the degree of cells in the anterior chamber after the application of 4 weeks of difluprednate 0.05% in 79 subjects submitted to phacoemulsification compared to an efficiency ratio of 77.5% with the use of 1% prednisolone. [53]

According to the previous calculation, the result is 74 eyes per group. The total when considering 2 intervention groups is 148 eyes, which was increased by 20% (30 eyes) for the probable losses. The total sample size required is 178 eyes. **Total n = 178 eyes.**

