8.3 Statistical methodology

8.3.1 Analysis of primary and secondary outcome variables

The statistical analysis will be carried out by personnel of Sophia Laboratories. The statistical program SPSS version 19 will be used.

The designated personnel will be blinded to the intervention groups. The coding will be done using consecutive numbers for each intervention group.

The data will be collected and sorted in an excel sheet. Later they will be exported to the platform of the SPSS program. The variables will be categorized according to their nature.

The results of the continuous quantitative variables will be presented in measures of central tendency: mean, standard deviation and ranges. See **Table 5 Variable measurement method**. The total size of the samples will consider an eye as a case for the evaluation of the efficacy.

The normal distribution of results will be obtained through the Kolmogorov-Smirnov and Shapiro-Wilks test, as applicable.

The statistical analysis of the continuous quantitative variables to find significant differences (p) will be the following:

. Inter-group analysis: t test for paired samples.

. Intra-group analysis: Mc Nemar test. Cellularity assessments in the anterior chamber will be considered for the analysis before the application of the intervention and in the final visit. The level of difference to consider significance will be of an alpha of 0.05 or less.

The result of nominal and ordinal qualitative variables will be presented in frequencies, proportions and percentages. See **Table 5 Method for measuring variables**

The statistical analysis to identify significant differences of the qualitative variables will be done by creating 2x2 contingency tables and will be done as follows:

- Difference between groups: χ^2 test (Chi-square) of Pearson or Fisher's exact in expected values less than 5.
- Intra-group analysis: Mc Nemar test.

The level of difference to consider significance will be an alpha of 0.05 or less.

For the reporting of adverse events all eyes of those participants who were randomly assigned to an intervention group will be considered. The results will be expressed in number of cases.

The final report of the results will be shown in tables or graphs, as appropriate.

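### The safety and tolerability comparison with prednisolone rests on a 0.05 test for symptoms and bare counts for adverse events, with no interval to show how much worse PRO-145 could be

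*Combined protocol and SAP*

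**What the plan says.** Section 5.6.1 states the aim of evaluating the efficacy, safety and tolerability of PRO-145 and to "compare it against the safety, tolerability and efficacy profile of commercially available steroid administration". Section 5.5.3 lists the safety and tolerability objectives separately for each arm.

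Section 6.4.3.4 records each post-instillation symptom (burning, pruritus, foreign body sensation, blurred vision) as present or absent. These are therefore qualitative variables under section 8.3.1. That section plans frequencies, proportions and percentages, and a between-group 2x2 comparison by chi-square, "Pearson or Fisher's exact in expected values less than 5". The decision rule is: "The level of difference to consider significance will be an alpha of 0.05 or less". The Summary repeats the method.

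For adverse events, 8.3.1 says that all randomised participants count and that the results are numbers of cases. It names no test for them. Section 8.3.3 puts everyone exposed at least once into the safety assessment.

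No confidence interval, bound or margin is planned for any safety or tolerability outcome. The only mention of 95% confidence is in the efficacy sample size (6.6.1): "With a statistical confidence of 95% corresponding to the type I error, equal to 1.96, with a power of 80"%.

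Section 5.3.1.3 summarises the sponsor's phase I study of 27 healthy subjects in three groups. It reports no statistically significant differences and no pressure rise in any subject, and then: "It was concluded that the safety profile of PRO-145 in equal circumstances is similar to that of Durezol".

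**The concern.** A test against 0.05 answers one question: is there evidence of a difference? A reader comparing two safety profiles needs another answer as well: how large an excess on the new product is still compatible with the data? Without an interval, a non-significant symptom comparison leaves that unanswered. For adverse events the gap is wider, because two counts side by side carry no planned comparative measure at all.

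The phase I summary makes this more than a formality. The sponsor moved there from no significant differences, in a small study, to a statement of similar safety. If the same reasoning were applied to this trial, a non-significant p-value could be taken as reassurance that it does not give.

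**Working it through.** **The plan's own figure.** There is none for safety or tolerability. The only sample size calculation is for efficacy (78.9% v 77.5%). Whether its 74 per group follows from those inputs is a separate matter and does not enter here. What is needed is the number per arm: 2 × 74 = 148, plus 30 for losses = 178, and 178 / 2 = 89.

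**Inputs**
- n = 89 per arm (6.6), 1:1 (7.1). This is the upper limit of the safety set in 8.3.3; 74 is shown as a lower case.
- Rule: uncorrected Pearson chi-square, or Fisher's exact test if an expected count is below 5; significant if p ≤ 0.05, two-sided (8.3.1; 6.6.1 uses 1.96).
- Symptom rates: assumed, because the documents give none. Each subject contributes one yes/no value.

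**Step 1: chance of missing a doubled rate.** For each pair of true rates (p_C, p_T), all outcomes (x, y) of two independent binomials are enumerated, the rule is applied to each, and

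miss = 1 − Σ P(x | n, p_C) · P(y | n, p_T) over the outcomes declared significant.

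| Prednisolone | PRO-145 | Missed, 89 per arm | Missed, 74 per arm |
|---|---|---|---|
| 5% | 10% | 77% | 80% |
| 10% | 20% | 54% | 60% |
| 15% | 30% | 33% | 40% |
| 20% | 40% | 16% | 23% |
| 30% | 60% | 2% | 3% |

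The even-chance point lies at a comparator rate of about 11% with 89 per arm and about 13% with 74.

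**Step 2: what a non-significant result can conceal.** Take 9/89 (10.1%) on prednisolone and 18/89 (20.2%) on PRO-145.

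- Pooled proportion: 27/178 = 0.1517. Standard error = √(0.1517 × 0.8483 × 2/89) = 0.0538. z = 0.1011/0.0538 = 1.88, so p = 0.060: not significant.
- Wilson 95% limits: 5.4% to 18.1% for 9/89, and 13.2% to 29.7% for 18/89.
- Newcombe lower limit: 10.1 − √[(20.2 − 13.2)² + (18.1 − 10.1)²] = −0.5 points.
- Newcombe upper limit: 10.1 + √[(29.7 − 20.2)² + (10.1 − 5.4)²] = +20.7 points.

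The plan would report percentages of 10.1 and 20.2 with p = 0.06. It would not show that an excess of about 20 points is still possible. Even equal counts (9 v 9) leave an interval of −9.3 to +9.3 points.

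**Step 3: would more patients be the remedy?** For 80% power, a doubling needs about 435 per arm from 5% and 199 per arm from 10%. That is out of proportion for a trial sized on efficacy. The remedy is to report the uncertainty.

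**The case against.** Several points count against a strong form of this concern.

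- **Safety is not the primary question.** The stated hypothesis concerns anterior chamber cells, the safety objectives are written for each arm separately, and the plan claims no safety power. Low power for uncommon events is normal in a trial of this size. This stands, and it limits the weight of the point. It does not remove the comparison promised in 5.6.1.
- **The p-value is not the only output.** Proportions are already planned for symptoms, and a reader could compute an interval from them. This is true. An interval that is not prespecified need not be reported, however, and adverse events are promised only as counts.
- **Symptoms such as burning or blurred vision may be common.** If so, a doubling would usually be found. This stands. A reader might infer that any doubled rate would usually be missed; the documents give no rates to support that, and the table shows that it fails from about 11% upward.
- **No rule equates non-significance with similarity.** This is correct. A reader might infer that the sponsor will report such a result as comparable safety, but for this trial that is inference. The phase I conclusion also cites the absence of pressure rises, is limited to equal circumstances, and concerns another difluprednate 0.05% product rather than prednisolone. Section 5.4 carries forward only a product "which has demonstrated an acceptable safety profile in preclinical and clinical phase I studies"; its word for similarity refers to bioavailability in animals.
- **The 0.05 rule is not stated for adverse events.** This is also correct. The argument about missed differences applies to the symptoms. For adverse events the defect is the absence of any comparative measure.

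**Conclusion.** The point holds in a limited form. The plan promises a safety and tolerability comparison but specifies nothing that bounds the possible excess on PRO-145: a 0.05 test for symptoms and counts for adverse events. For a comparator rate of about 10% or less, a doubled symptom rate is missed more often than found (77% at 5% v 10%, 54% at 10% v 20%). For commoner symptoms the test usually detects it. These figures assume 89 per arm, one yes/no value per subject and illustrative rates. The lack of an interval does not depend on the rates.

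No conclusion is drawn here on how well intraocular pressure and visual capacity would be compared. It is tempting to call them adequately powered, but that presumes an independent-groups t test, whereas 8.3.1 names a paired test between groups. That is a separate error. Nor do the documents support rewriting the phase I result: 5.3.1.3 is a short summary of another study and does not give its group sizes.

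This is a worthwhile and cheap improvement. It does not affect the primary efficacy analysis.

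**What to change.** In section 8.3.1 and in the Summary:

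1. For each post-instillation symptom, and for subjects with at least one adverse event, report both arms' proportions and the risk difference (PRO-145 minus prednisolone) with a 95% confidence interval by Newcombe's method.
2. For intraocular pressure and visual capacity, report the between-arm mean difference with a 95% confidence interval from an independent-groups analysis.
3. Add a sentence to this effect: *A non-significant difference will not be reported as similar or comparable safety or tolerability; the conclusion will state the confidence limit on the side unfavourable to PRO-145.*

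Sections 5.3.1.3 and 5.4 can stay as they are.

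The cost is protocol wording and a few intervals from data already collected, with no new patients, visits or procedures. The one drawback for the sponsor is that the safety statement becomes a bounded one, less favourable than a report of no difference.

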8.3.2 Additional analyzes

An internal analysis will be made to know the changes that occur between each visit. It is the sponsor's prerogative to request an additional analysis of the data, during the conduction of the study or at the end of this.

8.3.3 Population analysis and management of missing data

The effectiveness analysis will consider those cases in which the measurements of the baseline and final visit are met. Those subjects who do not comply with any of these measurements will not be integrated into the final database to evaluate the effectiveness. Nevertheless, an intention to treat analysis (ITT) will be carried out.

The safety assessment will include in the analysis all those subjects (considering one eye or both) who have been exposed at least once to any of the interventions regardless of the visit in which they were eliminated from the study.

9. Methods Monitoring

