5.5.2 Specific objectives

- Evaluate the efficacy of PRO-145 through the elimination of anterior chamber cellularity (CCA) at the final visit.
- Evaluate the efficacy of prednisolone acetate 1% by means of the elimination of CCA in the final visit

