Medication counting is another way to measure adherence. Classically referred to as "pills counting", in ophthalmology it is translated to the weight of the bottle. This is a simple, economical and non-invasive method. The main disadvantages of this method are: 1. The application of the medication can not be confirmed (it could have been intentionally thrown or instilled outside the eye) and 2. It depends on the subject bringing the medication back. [62] [63]

The approach with multiple procedures for measuring adhesion is recommended. Because there is no ideal adhesion measurement, it is appropriate to use more than one method when trying to achieve results that resemble reality. Selecting two or more methods allows their strengths and weaknesses to be compensated, in order to more reliably capture adherence levels. [61]

- The evaluation of the adherence by means of the diary of the subject will be carried out in the following way:

$$Ad = (A_r)100/A_i$$

Where:

Ad = Adherence

Ar = Applications registered in the first 14 days of treatment.

Ai = Applications indicated for the intervention in the first 14 days of treatment.

At the sponsor's facilities, the bottles will be weighed at the beginning and at the end of the study. The adhesion will be calculated considering: the weight of the empty bottle, the weight of the drop, the weight of the bottle with the content, the calculation of the total of drops to be applied during the entire time of intervention and the total weight of the drops applied. The following simplified formula will be used:

$$Ad = \frac{(P_i - P_f)100}{P_T}$$

Where:

Ad = adhesion

IP = weight of the bottle delivered to the subject at the start

Pf = weight of the bottle returned by the subject

PT = weight of the posology indicated for the intervention.

$$P_T = (P_g)G$$

Where:

P_g = weight of the drop of the intervention, determined by the department of research and development

G = number of drops indicated for the intervention

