There is no standardized parameter to define an adequate adherence, it must be defined and outlined by the objectives of the research in particular. [62] The efficacy of ophthalmic steroids is based on two fundamental principles: 1) The specific type and location of the inflammation determines the appropriate route of administration and 2) The treatment should be instituted as soon as possible, and the dose should be high enough and administration frequent enough to suppress inflammatory activity. According to the therapeutic utility curve, to establish the limits of the therapeutic window, a dosage regimen is required in which 50% of the established doses are exceeded, in order to achieve a pharmacological effect. A therapeutic regimen below this value is expected a lack of efficacy. Therefore, an adherence of over 60% according to the weight of the bottle ensures that it remains within the limits of efficacy of the therapeutic window established in the protocol. [64] [65] [66] For the efficacy analysis, only subjects with a minimum adherence of 80% by means of the subject's daily tool and a minimum of 60% by the weight of the bottle will be considered. The variation in the percentage of the measurement method has been chosen empirically to counteract the sensitivity and specificity of the same. It is estimated that with a minimum adherence of 60% the intervention can exert its expected anti-inflammatory pharmacological action. [44]

6.3.3 Treatments and concomitant interventions allowed and prohibited before and during the study.

The subjects admitted correctly to the study, who meet the eligibility criteria, may continue with the systemic treatment of the underlying diseases. If during the development of the study they require the implementation of a new permitted medication, they may do so. All concomitant medications used must be duly reported in the notes of the clinical file and in the corresponding section.

Allowed medications:

- Ophthalmic:
- All permitted medications applied via ophthalmic during the study, must wait a minimum period of 10 minutes from the last application of the treatments under study or reference. The foregoing in order to avoid the interaction of the treatments in the tear film, based on the tear flow index and the physiological tear volume. [67]
 - Tetracaine 0.5%
 - Tropicamide 0.8% / Phenylephrine 5%
 - Any antibiotic
 - Beta-blockers
 - Alpha agonists
- Administered by a different route to ophthalmic:

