8.1.1 Strategies to complete the follow-up

- You will be informed in a clear way the importance of the study and the benefits that the population will obtain from the results of the study.

- Transportation assistance will be provided in order for the participant to attend their visits.
- A printed calendar will be provided with the objective of reminding the participant of their appointments and the activities that will be carried out, in addition to the estimated duration of the same.
- In case the participant does not attend his / her appointment, the research center must make a call to know the reason and try to arrange a new appointment within the established window period or an unscheduled appointment.
- In case it is not possible to make an appointment, it will be asked about the presence of adverse events and the reason for leaving the study, as minimum data.

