10.5 Deviations

A deviation is any alteration in the procedures and activities described in the research protocol approved by the committees and regulatory authorities. They may be the product of modifications or omissions, which may compromise the safety of the participants or the quality of the data generated.

- **Major deviation / violation:** is one that impacts one or more of the following aspects:
- Subject security
- Alteration of the risk-benefit balance
- Commit the integrity of the study data
- It affects the voluntariness of the subject in the participation of the study.

The list of examples cited below serves the purpose of guidance, but does not cover all possible cases, so it is not limiting:

- I. **In relation to informed consent:** 1) that informed consent has been taken by an unauthorized person to do so, 2) that the subject under investigation signs a version of informed consent not approved by the committees and regulatory entity, 3) that perform a study procedure prior to signing the informed consent.
- II. **Regarding the inclusion / exclusion criteria:** 1) enroll subjects who do not meet all the inclusion criteria and / or meet any exclusion criteria, 2) enroll defined subjects as part of

- the so-called vulnerable population: children, pregnant women, prisoners, without prior approval for such group; 3) Enroll patients before the start or after the end of the study.
- III. **In relation to the medication of the study:** error in the delivery or dosage of the same.
 - IV. **In relation to concomitant medication:** use of prohibited medication.
 - V. **Regarding the study procedures:** that those who, in the opinion of the principal investigator, compromise the safety of the research subject are not carried out.
 - VI. **In relation to the reporting of serious adverse events:** those that are reported outside the time stipulated by the committees.

Minor deviation: is that which does not impact on the safety of the subject, does not alter the risk-benefit balance, does not compromise the integrity of the study data or does not affect the subject's willingness to participate in the study.

The list of examples cited below serves the purpose of guidance, but does not cover all possible cases, so it is not limiting:

- I. I forget about taking the study medication.
- II. Lack of return of study medication by the subject.
- III. Visits of the research subject carried out outside the window.

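### The efficacy analysis is limited to adherent completers, and the added ITT analysis has neither a rule for a missing final anterior chamber cell grade nor an explicit rank

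*Combined protocol and SAP*

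**What the plan says.** Two sections restrict the efficacy set.

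- **Section 8.3.3** requires both the baseline and the final measurement, and adds: "Those subjects who do not comply with any of these measurements will not be integrated into the final database to evaluate the effectiveness".
- **Section 6.3.2** sets adherence thresholds: "For the efficacy analysis, only subjects with a minimum adherence of 80% by means of the" diary, together with "a minimum of 60% by the weight of the bottle will be considered".

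Neither section mentions the other. Section 8.3.3 then adds: "Nevertheless, an intention to treat analysis (ITT) will be carried out". That sentence is all the plan says about ITT. Section 8.3.1 lists tests, and section 8.3.2 covers visit-to-visit changes and further analyses at the sponsor's request.

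Other relevant text:

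- The first specific objective (5.5.2) is "Evaluate the efficacy of PRO-145 through the elimination of anterior chamber cellularity (CCA) at the final visit". The second says the same for prednisolone. Both are within-arm aims.
- On bottle weighing, section 6.3.2 concedes: "It depends on the subject bringing the medication back". Section 10.5 lists "Lack of return of study medication by the subject" as a minor deviation.
- When a missed visit cannot be rescheduled (8.1.1), "it will be asked about the presence of adverse events and the reason for leaving the study, as minimum data".
- Section 6.2.3 eliminates subjects for a serious adverse event, or for an adverse event that the investigator judges a threat to health and that needs a medicine outside the protocol. Section 9.3.1.1 has lack of therapeutic response recorded as an adverse reaction.

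**The concern.** Treatment is assigned at the baseline visit (6.5.2.1). Attendance at the final visit and adherence over the treatment period come later and may depend on how the eye is doing. The baseline measurement is different: it is taken at the assignment visit, so requiring it is not a post-randomisation restriction.

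The documents give a route by which poor outcome could lead to a missing final grade. An eye that responds poorly may generate an adverse event, the event may call for an unauthorised medicine, and the subject is then eliminated. If subjects who leave clear less often than those who stay, clearance among completers is too high in that arm. The bias needs no imbalance between arms, and it falls on the quantity that the specific objectives name. The between-arm comparison in section 8.3.1 is exposed only if loss differs by arm.

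The ITT sentence could correct this, but it cannot be carried out reproducibly as written. Two analysts could treat a missing final grade differently and both comply with the plan.

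**Working it through.** **Fitting the two restrictions together.** Each is a necessary condition, and they are compatible: together they describe adherent completers. One group cannot be placed. Bottle adherence is (starting weight − returned weight) × 100 / weight of the prescribed drops. Without a returned bottle there is no returned weight, so the 60% rule can be neither met nor failed.

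**The plan's loss allowance (6.6.1).** Taking 74 per group as given: 2 × 74 = 148; 148 × 1.20 = 177.6, rounded to 178; 178 − 148 = 30 eyes, which is 30/178 = 16.9% of those enrolled. An equal split is 15 of 89 per arm. Section 6.6.1 does not say whether these losses include adherence exclusions. Below, all 30 are assumed to lack a final grade.

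**Rates.** The planning rates in 6.6.1 (78.9% and 77.5%) describe reduction in cell grade. I assume they apply to clearance among observed eyes. Number cleared = rate × eyes observed, rounded.

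**Within an arm, 15 lost.** Observed: 0.789 × 74 = 58.4, so 58/74 = 78.4%. Over all 89 eyes, clearance = (58 + number cleared among the 15)/89:

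- none of the 15 cleared: 58/89 = 65.2%, the lower limit for this loss;
- half cleared: (58 + 7.5)/89 = 73.6%.

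The largest possible overstatement is therefore 78.4 − 65.2 = 13.2 points.

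**Between arms.** Pearson chi-square without correction, PRO-145 first, one rule applied alike to both arms:

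| Lost (assumed) | Complete cases | Lost = failure |
|---|---|---|
| 15 v 15 | 58/74 v 57/74: +1.4, p=0.84 | 58/89 v 57/89: +1.1, p=0.88 |
| 10 v 20 | 62/79 v 53/69: +1.7, p=0.81 | 62/89 v 53/89: +10.1, p=0.16 |
| 7 v 23 | 65/82 v 51/66: +2.0, p=0.77 | 65/89 v 51/89: +15.7, p=0.028 |
| 23 v 7 | 52/66 v 64/82: +0.7, p=0.91 | 52/89 v 64/89: −13.5, p=0.059 |
| 24 v 6 | 51/65 v 64/83: +1.4, p=0.84 | 51/89 v 64/89: −14.6, p=0.042 |

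So the threshold is about 7 v 23 in one direction and 24 v 6 in the other. Fisher's exact test gives p=0.040 and p=0.060 for those two, so the second is borderline. Counting lost eyes as cleared does not reach significance at any split of the 30 (smallest p=0.12).

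**How likely is such a split?** If true loss were equal, comparing 7/89 with 23/89 gives p=0.0014.

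**The case against.** The strongest reply is that the plan already commits to an ITT analysis, and that its opening word, after the restricted set has been called the effectiveness analysis, signals that ITT is supplementary. A per-protocol set is legitimate, and the analysts are blinded (7.4 and 8.3.1). ITT can also use the observed final grades of subjects excluded for low adherence, so the missing-data gap concerns only those with no final grade.

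Much of this stands. But if ITT is supplementary, the selected set leads, which is the difficulty. Blinding limits steering toward a product; it does not remove selection or supply a rule.

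Three stronger readings are tempting and are not supported:

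- **The missing-data rule decides the comparison.** A reader might bracket the difference by counting the 15 lost eyes as failures in one arm and cleared in the other: (58 − 72)/89 = −15.7 to (73 − 57)/89 = +18.0 points. That needs opposite rules for the two arms. Under one common rule, significance changes only with the extreme splits above. Both arms are masked topical steroids on the same four-times-daily schedule for 14 days, and nothing in the documents predicts such imbalance.
- **An unreturned bottle excludes the subject.** The text leaves that subject unclassified, not excluded.
- **The two restrictions contradict each other.** They do not; they lack a cross-reference.

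It is also fair that counting lost eyes as failures can mislead. It turns unequal loss into an apparent effect, and at equal loss it draws the arms together (+1.4 to +1.1 points), which matters if the aim is similarity to prednisolone.

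**Conclusion.** The point holds, chiefly for clearance within each arm. The plan conditions its efficacy analysis on final attendance and adherence, and leaves ITT without a missing-grade rule or an explicit rank. At the plan's own loss allowance, split equally, completer clearance of 78.4% could correspond to as little as 65.2% of randomised eyes. That is an upper bound on the bias, not an expected value. The actual size depends on how many eyes lack a final grade and how they fared, and the documents give neither. The difference between arms is little affected unless loss is markedly unequal.

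The figures assume that the 6.6.1 rates describe clearance and that all 30 allowance eyes lack a final grade; the unequal splits are illustrations only. This is a cheap improvement to the plan, not a defect that invalidates the comparison.

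**What to change.** In section 8.3.3, with a cross-reference from 6.3.2:

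1. Make the lead efficacy analysis all randomised subjects by assigned arm, using every observed final CCA grade whatever the adherence or bottle return.
2. Before unblinding, fix one rule for a missing final grade, applied alike to both arms (for example, counted as not eliminated).
3. Name one sensitivity analysis under a different rule, such as imputation from the visit 1 and visit 2 grades.
4. Report loss and its reasons by arm.
5. Report adherent completers as a per-protocol analysis, and say how an unreturned bottle is classified. If the aim is similarity to prednisolone, show both sets side by side.

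The cost is wording only. The visit 1 and 2 grades are already scheduled (6.4.4), and the reason for leaving is already asked for (8.1.1). There are two downsides. Reported clearance will be somewhat lower. A rule that counts lost eyes as failures is sensitive to unequal loss, which is why items 3 and 4 belong with it.
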